5.1.3 Pooling of centers

All tables will be presented in total over all participating countries and centers. The distribution of number of patients per country will be present in the disposition section of the report.

5.2 Demographic and other background data

5.2.1 Basic description

The disposition of subjects (cf. Section 4) will be tabulated by treatment and for the entire population. Details on protocol deviations will be listed.

Discontinued patients will be described by frequency distributions including the reasons and in individual listings.

Demographic data (gender, age (categorical and continuous), weight, height, body mass index (BMI), race, ethnic group) will be summarized in tables and presented for the SAF, FAS and PP2 population stratified by treatment group. Other baseline or background data, e.g. disease-specific information, will comprise descriptive tables for the SAF and PP2 population for the following variables:

- Smoking status at screening and randomization
- Alcohol consumption at screening and randomization
- Vital Signs (Systolic and diastolic blood pressure, pulse and body temperature) at screening and randomization
- ECG evaluation (normal/abnormal)
- Physical examination (normal/abnormal)
- Gout History and CV Risk Score

The following background data will only be listed:

- Medical history

STATISTICAL ANALYSIS PLAN

Protocol No: MEIN/14/FEB-PWV/001 (FORWARD)

Version Number: 2.0

Date of Issue: 2018-03-16

Page 16 of 22

- Prior and concomitant procedures and surgeries (except those noted under Cancer treatment history)
- Childbearing potential and urine pregnancy test

5.3 IMP exposure, compliance

Treatment compliance will be monitored from Visit -1 to Visit 4 (end of study treatment).

The amount of study medication taken by the subject will be derived by counting the number of tablets dispensed and returned in the blister which will be recorded in the eCRF.

The patient compliance for the study treatment period is calculated as described in section 8.1.

A patient who has taken at least 60% and no more than 120% of the required study drug intake since the last visit will be considered compliant.

All IMP treatment details will be listed.

5.4 Medical history, physical examination

Data on medical history and physical examination will be listed. Medical history will be coded according to the Medical Dictionary for Regulatory Activities (MedDRA). Codes will be reviewed by a Medical Expert and approved by the sponsor before data base lock.

5.5 Prior and concomitant medication

Any relevant medication ended within the screening period will be defined as 'Prior Medication' and will be summarized separately. Concomitant medications (medications started after the screening date) and Prior and Concomitant medications (medications started during the screening period but ended after this period or still ongoing will be summarized all together.

All details of prior and concomitant medications will be listed including, the route, dose, frequency, start and stop date and indication.

Medications will be coded using the WHO DD thesaurus in the version current at the time of database lock. Coding will be performed by the CRO and agreed upon with the sponsor before data base lock. (cf. DMP). For concomitant medications tables will show the frequencies of subjects by WHO DD preferred term. Prior medication will only be listed.

5.6 Concomitant non-pharmacological measures, pre-medication

Not applicable.

STATISTICAL ANALYSIS PLAN

Protocol No: MEIN/14/FEB-PWV/001 (FORWARD)

Version Number: 2.0

Date of Issue: 2018-03-16

Page 17 of 22

5.7 Efficacy

The efficacy evaluation of the primary endpoint will be performed in both FAS and PP Populations. The Full Analysis Set (FAS) will be the primary analysis population for the confirmatory analysis. A sensitivity analysis based on the Per-Protocol 2 (PP2) population will be performed.

5.7.1 Primary endpoint

The primary efficacy endpoint is Pulse Wave Velocity (PWV) after 36 weeks of treatment with febuxostat or allopurinol.

At least two PWV measurements will be taken per visit. The evaluation of measurements will be performed by two independent laboratory teams. Values valid to be included in analysis will be selected by experienced medical experts. Details on processes related to the assessment and final selection of the PWV/PWA reports that will be used for the statistical analysis are described in the document named: “PWV/PWA reconciliation process” section 15.5 Appendix E of Data Management Plan. Mean values from all measurements considered to be valid will be calculated per visit and will result in one value per visit per parameter.

Analysis of covariance (ANCOVA) with the 36 weeks PWV value as dependent variable, treatment group as factor and age, baseline blood pressure, baseline PWV as covariates, will be used to compare the efficacy of the two treatment groups.

The assumptions of the underlying model such as normality of residuals and homogeneity of variance will be investigated using significance level of 0.1.

All covariates found not to be statistically significant at the 0.05 two-sided significance level, will be removed from the model and the final model will only include statistically significant covariates.

For covariates found to be significant, the treatment by covariate interaction will be evaluated using ANCOVA model with the terms for treatment, covariate and treatment by covariate interaction.

If interaction is statistically significant at the 0.1 two-sided significance level, additional analyses will be performed to explore the interaction.

A sensitivity analysis with the change from baseline to Week 36 as response variable will be performed similarly to the primary analysis.

The relationship between PWV at Week 36 (change from baseline to Week 36) and febuxostat as well as allopurinol dose will be explored using scatterplots.

The LOCF method will be utilized for missing data imputations as described in section 5.1.2.

STATISTICAL ANALYSIS PLAN

Protocol No: MEIN/14/FEB-PWV/001 (FORWARD)

Version Number: 2.0

Date of Issue: 2018-03-16

Page 18 of 22

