2.3 Study design

This study is designed as a randomized, active-controlled, open label, evaluator blind, parallel group, multi-center, multi-national, Phase IV trial. Patients will be randomized 1:1 to receive febuxostat or allopurinol.

There will be approx. 35 sites in the following countries: Germany, the Netherlands, Italy, Poland, Serbia, Romania.

Study duration for individual patients will be 39 weeks. This includes a one-week run-in/screening period which can be extended to max 30 days in case of re-testing, followed by a 36 weeks treatment and a 2 weeks safety follow-up (by phone call).

The study physician responsible for randomization and drug supply handling is unblinded to study medications and therefore will not be involved in the main efficacy evaluations of each patient randomized in the study.

Conversely, the study physician/s responsible for the main efficacy evaluation (Pulse Wave Velocity) will be blind to study treatments. In addition, key efficacy variables will be performed by an independent core laboratory where the central reader will be blind to the treatment assigned to patients.

Fasting lipid levels, NTproBNP, BNP, markers of inflammation and endothelial activation/adhesion, oxidative stress parameters, eGFR, changes in urine albumin excretion as evaluated by first morning albumin/creatinine ratio will be also measured by a central laboratory.

Eligible patients will be randomized to treatment with allopurinol 100 mg or febuxostat 80 mg (1:1 ratio). Up-titration of allopurinol or febuxostat to the maximum dose permitted in the study may be performed between Week 2 and Week 10, see flow chart below for details.

A follow-up safety assessment will be performed by a phone call 2 weeks after study termination.

STATISTICAL ANALYSIS PLAN

[figure not shown]
Protocol No: MEIN/14/FEB-PWV/001 (FORWARD)

Version Number: 2.0

Date of Issue: 2018-03-16

Page 10 of 22

Trial flow chart

Notes:

	Day -30 to Week -1	Day 0	Week 2 ± 4 days	Week 12 ± 4 days	Week 24 ± 4 days	Week 36 ± 4 days	Week 38 + 3 days after
	Visit -1	Visit 0	Visit 1	Visit 2	Visit 3	Visit 4	Visit 5 Phone call
	Screening	Randomization	On Treatment Visit	On Treatment Visit	On Treatment Visit	End of Study visit	Safety Follow up
Inclusion/exclusion crit.	X						
Informed consent	X						
Randomization		X					
Medical history	X						
Concomitant medications	X	X	X	X	X	X	
Physical examination	X			X	X	X	
Vital signs (BP, HR body temperature)	X	X		X	X	X	

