2.4 Planned sample size

A sample size of 79 in each group will have 85% power to detect a difference in means of 1.8 m/sec at Week 36 assuming that the common standard deviation is 3.75 m/sec using a two group t-test with a 0.05 two-sided significance level. Expecting a drop-out rate of approximately 15%, the total number of subjects to be randomized in order to achieve the planned sample size will be 91 per treatment arm, in total 182.

STATISTICAL ANALYSIS PLAN

Protocol No: MEIN/14/FEB-PWV/001 (FORWARD)

Version Number: 2.0

Date of Issue: 2018-03-16

Page 12 of 22

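### The primary ANCOVA drops non-significant covariates, so the Week 36 data decide its covariate set and the supporting analyses may use different sets; the numerical impact is small

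*SAP*

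**What the plan says.** SAP section 5.7 makes the FAS analysis of PWV confirmatory and adds a sensitivity analysis in PP2. Section 5.7.1 sets up the ANCOVA of Week 36 PWV with "treatment group as factor and age, baseline blood pressure, baseline PWV as covariates". It continues: "All covariates found not to be statistically significant at the 0.05 two-sided significance level, will be removed from the model". The reduced model is then the final one. No covariate is exempt, not even baseline PWV, and the SAP does not say whether removal is done in one step or one covariate at a time.

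Section 5.1.2 plans LOCF for the primary endpoint and, as robustness checks, imputation by treatment-group means and no imputation. Section 5.7.1 adds: "A sensitivity analysis with the change from baseline to Week 36 as response variable will be performed similarly to the primary analysis". None of these passages says whether the covariates selected in the FAS are carried over or selected afresh.

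For comparison, section 5.7.2 fixes the ANCOVA for the continuous secondary endpoints (treatment and the respective baseline value) with no removal rule. Of the ANCOVAs in section 5.7, only the PWV analysis of section 5.7.1 lets the data choose the covariates.

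**The concern.** A covariate's p-value in one trial is a poor guide to whether it is needed. Adjustment for a prognostic baseline variable removes chance imbalance from the treatment estimate, and dropping the variable because it missed 0.05 lets that imbalance back in. Three things are at stake.

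- **The confirmatory test.** The reported estimate, SE and p-value come from a covariate set picked using the outcome.
- **The supporting analyses.** If the rule is applied afresh in PP2 or under another way of handling missing data, a changed result may come from the covariates rather than from the patients or the imputation.
- **The change-score analysis.** With baseline PWV in the model it cannot give a different treatment effect, so agreement with the primary result is no evidence of robustness.

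**Working it through.** **1. The plan's own figure.** Section 2.4 states: "A sample size of 79 in each group will have 85% power to detect a difference in means of 1.8 m/sec at Week 36". Its other inputs are an SD of 3.75 m/s and an unadjusted t-test at two-sided 0.05. By the normal approximation, n = 2(1.960 + 1.036)² × (3.75/1.8)² = 2 × 8.98 × 4.34 = 77.9, so 78 per arm. The exact t-test has 84.59% power at 78 and 85.04% at 79, so 79 is reproduced. The calculation uses no covariates, so fixing the covariate set leaves the sample size unchanged.

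**2. Number of possible models.** Three covariates, each kept or dropped: 2³ = 8.

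**3. How often the data change the model.** Simulation with 182 randomised 1:1, 15% dropout and 4,000 trials per row.

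Assumptions not in the SAP:
- standardised coefficients as shown in the table;
- covariate correlations 0.2-0.4;
- residual Week 12 to Week 36 correlation 0.5;
- dropouts carry Week 12 forward;
- a further 10% excluded at random to imitate PP2;
- one-step removal.

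The group-mean analysis was not simulated. Entries are % of trials, except the last column.

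| PWV / age / BP coefficient | True difference (m/s) | Age kept | BP kept | Set differs: no imputation | Set differs: PP2 | Significant: fixed | Significant: selected | Verdict changed | Mean shift (m/s) |
|---|---|---|---|---|---|---|---|---|---|
| 0.6 / 0.10 / 0.10 | 0 | 37.8 | 39.8 | 23.2 | 29.8 | 5.1 | 5.3 | 1.0 | 0.030 |
| 0.6 / 0.15 / 0.15 | 0 | 76.4 | 78.2 | 21.4 | 30.5 | 5.5 | 5.5 | 0.4 | 0.013 |
| 0.4 / 0.15 / 0.10 | 0 | 55.4 | 30.9 | 24.1 | 31.1 | 4.8 | 5.0 | 1.0 | 0.033 |
| 0.7 / 0 / 0 | 0 | 4.7 | 5.6 | 7.7 | 8.8 | 4.9 | 5.0 | 0.6 | 0.026 |
| 0.9 / 0 / 0 | 0 | 5.1 | 4.9 | 7.0 | 8.8 | 5.0 | 5.1 | 0.8 | 0.016 |
| 0.6 / 0.10 / 0.10 | 1.0 | 39.6 | 40.9 | 24.0 | 30.3 | 68.7 | 68.3 | 2.4 | 0.028 |
| 0.4 / 0.15 / 0.10 | 1.0 | 56.0 | 30.8 | 23.5 | 30.1 | 53.0 | 53.3 | 2.7 | 0.032 |

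Monte Carlo error at 5% is √(0.05 × 0.95/4000) = 0.3 points, so no rejection rate under the null is clearly away from 5%. Across the four simulated analyses (LOCF, no imputation, PP2, change from baseline), at least one used a different covariate set in 11-36% of trials. One-step and stepwise removal chose different sets in 1-6%.

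**4. Size of the shift at the planned n.** Further simulations used 79 per arm, SD 3.75, assumed baseline-PWV slopes of 0.5-0.6 and modest age and blood-pressure effects.
- No covariate set was chosen in more than about 46% of trials.
- The 95th percentile of the shift in the estimate was 0.11-0.13 m/s, against a treatment SE of 0.44-0.49 m/s. That is 0.11/0.49 = 0.22 to 0.13/0.44 = 0.30 of an SE, and at most 0.13/1.8 = 7% of the design difference.
- The verdict changed in 0.5-0.9% of null trials and about 1-3% at 1.2 m/s.
- Among trials with a fixed-model p-value between 0.03 and 0.07, it changed in about 14-20%.

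**5. Change from baseline.** Write the primary model as Y = a + τT + γ₁Age + γ₂BP + βB + e, with B the baseline PWV. Subtracting B from both sides gives Y − B = a + τT + γ₁Age + γ₂BP + (β − 1)B + e. The residuals are the same, so the estimate of τ, its SE and its p-value are the same. Only the test on B changes, from β = 0 to β = 1. The analyses can therefore differ only if the rule removes B from at least one of them. At assumed slopes of 0.5-0.6 this did not happen. At 0.8 the treatment estimate differed in 0.4% of trials. At 0.9 the two analyses parted in about 5% to 24%, depending on the other settings; in the last null scenario of the table, B was kept in 76.3% of change-score fits and in every raw-value fit.

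**The case against.** The best defence is that the rule is itself written in advance. The candidates, the 0.05 threshold and the definition of the final model are all stated, and section 3.1 requires the SAP to be final before database lock and unblinding. That stands. A reader might infer that the primary analysis is unspecified, but the SAP does not support this: the algorithm is given, apart from the one-step or stepwise question, and only its output depends on the data.

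A reader might also expect an inflated false-positive rate, because the reported SE ignores the selection. The simulations show none of note, and power agrees to within 0.5 points.

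Thirdly, it is tempting to say that the rule is definitely re-run in every supporting analysis. The SAP does not say so, and its final model could be read as one model carried forward. For PP2 and the imputation analyses, different covariates are a possibility that the text leaves open.

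Lastly, one might claim that the change-score analysis always reproduces the primary result. It does so only while both models keep the same covariates, including baseline PWV. The SAP gives no baseline-to-Week 36 correlation from which to judge how often that would fail.

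None of this supplies a reason to let significance decide the adjustment.

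**Conclusion.** The concern holds as a point that should be fixed, not as a fatal flaw. The covariate set of the confirmatory analysis depends on the Week 36 data, and the supporting analyses may use other sets, which would blur what they show. The consequences are small on average: a shift of 0.01-0.03 m/s in the table's scenarios and about 0.1 m/s at the 95th percentile in the separate runs at the planned n. They matter mainly when the result is near the significance boundary. The change-score analysis adds no information while baseline PWV is kept; where it does differ, the difference comes from the removal rule.

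The algebra and the reading of the text need no assumptions. The percentages rest on assumed covariate effects and correlations that the SAP does not give, and should be read as a range.

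**What to change.** - Delete the removal sentence in section 5.7.1, with the clause that defines the reduced model as final.
- State that treatment, age, baseline blood pressure and baseline PWV stay in the model whatever their p-values, in the FAS, in PP2 and in every missing-data analysis.
- Name the blood-pressure component before unblinding. Section 5.7.1 says only blood pressure, while section 5.9.2 records systolic and diastolic values; the choice is the sponsor's.
- Report any reduced model as supportive only.
- Present the change-from-baseline analysis as a restatement of the primary result, not as a sensitivity analysis.

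With 158 patients, residual degrees of freedom are 158 − 2 = 156 with treatment alone and 158 − 5 = 153 with all three covariates. The cost is thus at most three, with no change to the sample size and no material loss of power in the simulations.

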4.4 Subgroup analyses

No subgroup analyses are planned.

STATISTICAL ANALYSIS PLAN

Protocol No: MEIN/14/FEB-PWV/001 (FORWARD)

Version Number: 2.0

Date of Issue: 2018-03-16

Page 14 of 22

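### Treatment-by-covariate interactions on Week 36 PWV are tested without the other prespecified covariates, and only after a significant main effect, so this exploratory check loses power

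*SAP*

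**What the plan says.** SAP section 5.7.1 analyses Week 36 PWV by ANCOVA with "treatment group as factor and age, baseline blood pressure, baseline PWV as covariates". It then simplifies the model: "All covariates found not to be statistically significant at the 0.05 two-sided significance level, will be removed from the model".

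Interactions come next and are conditional on that result. For the covariates found significant, "the treatment by covariate interaction will be evaluated using ANCOVA model with the terms for treatment, covariate and treatment by covariate interaction". The word covariate is in the singular and no other term is listed. The consequence of a positive test is limited: "If interaction is statistically significant at the 0.1 two-sided significance level, additional analyses will be performed to explore the interaction".

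Nothing else in the SAP covers these interactions. Section 4.4 says "No subgroup analyses are planned". The change-from-baseline sensitivity analysis in section 5.7.1 is to be done in the same way as the primary analysis, so it inherits the rule. The scatterplots in that section concern dose, not age, blood pressure or baseline PWV.

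**The concern.** There are two separate problems.

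1. **The model.** If two or three covariates are retained, the final model adjusts for all of them, but each interaction is tested in a smaller model. Variance that the plan has already chosen to remove returns to the residual. This matters most for age and blood pressure, because the omitted term is then baseline PWV, probably the strongest predictor of Week 36 PWV.

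2. **The condition for testing.** A significant average slope says nothing about whether the slopes differ between arms. When they run in opposite directions the average can be near zero. The covariate is then dropped and its interaction is not examined.

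At stake is how a clean result is read. If no interaction is reported, a reader may take the PWV effect as uniform across age, blood pressure and baseline stiffness, when the test was weak or was not run.

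**Working it through.** **Inputs from the SAP.** Section 2.4: 79 evaluable per arm (158 in total), SD 3.75 m/sec, difference 1.8 m/sec, two-sided alpha 0.05. Section 5.7.1: interaction level 0.10, retention level 0.05.

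**The plan's own figure.** Section 2.4 states "A sample size of 79 in each group will have 85% power to detect a difference in means of 1.8 m/sec". The noncentral t distribution gives power 0.850 at 79 per arm and 0.846 at 78, so 79 is reproduced. The SAP gives no figure for the interaction tests.

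**Assumptions.** The SAP states no prognostic strengths or correlations. Take standardized coefficients b for age / blood pressure / baseline PWV of 0.2/0.2/0.6, 0.1/0.1/0.7, 0.3/0.3/0.3 and 0.1/0.1/0.4, with common pairwise correlation 0, 0.3 or 0.5 (matrix R).

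**Loss of precision.** With v = b'Rb (variance explained by all three covariates) and c = Rb (correlation of each covariate with the outcome), the ratio of the interaction standard error in the three-term model to that in the full model is about

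sqrt[(1 − c²) / (1 − v)].

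Example with b = 0.2/0.2/0.6 and correlation 0.3:
- v = 0.04 + 0.04 + 0.36 + 2 × 0.3 × (0.04 + 0.12 + 0.12) = 0.608
- age: c = 0.2 + 0.3 × 0.8 = 0.44, ratio = sqrt(0.8064 / 0.392) = 1.43
- baseline PWV: c = 0.6 + 0.3 × 0.4 = 0.72, ratio = sqrt(0.4816 / 0.392) = 1.11

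Over the whole grid, starting from 80% power at 0.10 in the full model:

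| Interaction with | SE ratio | Power in three-term model |
|---|---|---|
| Age | 1.10 to 1.51 | 50% to 73% |
| Baseline PWV | 1.01 to 1.18 | 68% to 79% |

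Blood pressure has the same coefficient as age in every setting, so the age row applies to it too.

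A second simulation used different assumptions: age correlated 0.4 with baseline PWV and 0.3 with blood pressure, and baseline-to-Week-36 PWV correlations of 0.5/0.6/0.7/0.8. The treatment-by-age SEs were 0.594/0.587/0.583/0.575 in the three-term model and 0.529/0.487/0.437/0.366 in the full model. The ratios are 1.12/1.21/1.33/1.57. Together the two sets give an increase of roughly 10% to 55%.

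**Type I error.** With no interaction, the three-term model rejected in 9.2% to 11.1% of simulated trials, against a nominal 10%.

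**Effect of the main-effect condition.** Simulation with 4,000 trials per setting, correlation 0.3, and a slope difference between arms of 0.3 outcome SD per SD of age (0.3 × 3.75 = 1.125 m/sec):

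| Average age coefficient (b for blood pressure / PWV) | Full model, no condition | Three-term, no condition | Condition met | Three-term with condition |
|---|---|---|---|---|
| 0.2 (0.2/0.6) | 91% | 67% | 94% | 63% |
| 0.05 (0.1/0.7) | 87% | 61% | 15% | 9% |
| 0 (0.2/0.6) | 81% | 60% | 5% | 3% |

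With a clear average age effect the condition costs little beyond the reduced model. With a small or zero average effect it removes almost all detection.

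**The case against.** The strongest reply is that this step decides nothing. A significant interaction leads only to further exploration. The treatment estimate, its p-value and the confirmatory conclusion are unchanged. That stands, and it limits the weight of the point.

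Four further replies have some force:
- **Size of interaction.** A slope difference of 1.2 m/sec per SD of age moves the treatment effect by 2 × 1.2 = 2.4 m/sec between one SD below and one SD above the mean age, more than the 1.8 m/sec design difference. At 0.5 m/sec per SD, the SEs above and a normal approximation give power of about 22% in the three-term model. The full model gives 25%, 27%, 31% and 39% for the four correlations (for example 0.5 / 0.437 = 1.14, power 31%). The trial was sized for the main effect, and neither model detects a small interaction reliably.
- **Selected cases.** Age tested without baseline PWV is the unfavourable case, and a zero average effect is a special one. Baseline PWV loses little and will probably meet the condition.
- **Other readings.** The sentence may name only the terms of interest, with other retained covariates understood. If just one covariate is retained, the three-term model is the final model plus its interaction. The literal text does not say that others stay in, so clarification is still needed.
- **False flags.** The condition limits the number of tests. This is a real trade-off, addressed in the fix.

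A reader might go further and infer an inflated false-positive rate. The simulated null rates do not support that. A reader might also infer bias from chance differences between arms in how baseline PWV relates to age. Under randomization this is sampling noise already contained in the larger standard error, not a second fault.

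**Conclusion.** The point holds as a loss of power in an exploratory check. The wording in section 5.7.1 excludes the other prespecified covariates from each interaction model. Under assumed correlations this raises the treatment-by-age standard error by roughly 10% to 55%; blood pressure is affected for the same reason, and baseline PWV only slightly. The main-effect condition means that a covariate with opposing slopes would rarely be examined: about 5% of trials if its average effect is exactly zero, and about 15% in the setting with a small average effect.

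The direction follows from the structure of the rule. The sizes depend on assumed coefficients, correlations and an interaction that is large relative to the design difference. It would be wrong to infer that the primary result is at risk: the interaction step does not enter the confirmatory comparison.

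**What to change.** Replace the interaction sentence in section 5.7.1 with:

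> For each of age, baseline blood pressure and baseline PWV, regardless of the significance of its main effect, the treatment-by-covariate term will be added, one at a time, to the ANCOVA containing treatment and all three prespecified covariates, and tested at 0.1 as an exploratory check.

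Add that this model is used for the interaction check even if the final model drops covariates. Otherwise the new sentence conflicts with the removal rule just before it.

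The cost is wording only; the data are already collected. The downside is that three tests are always run. If they are independent and no interaction exists, the chance of at least one false flag is 1 − 0.9³ = 27%, which the exploratory label covers. Because the covariates are likely to be correlated, a flag on one may reflect an interaction with another, so any follow-up should look at all three together.
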